-Study schedule: Months 3-44 (see Timeline below)

-Time for participants: approximately 45 minutes

Treatment/Intervention Period. Participants will be randomly assigned in a 1:1 ratio to receive either the RCTM intervention or a usual care control condition. The project biostatistician ([name]) will generate a random assignment schedule using a random number generator provided by the SAS analysis system. Treatment condition assignments generated by this program will be printed and individual caregiver assignment slips will be placed in sequentially numbered, sealed opaque envelopes. The next sealed envelope in

SOCIAL PROTOCOL (HRP-580)

PROTOCOL TITLE: The Residential Care Transition Module

VERSION DATE: 2/10/2022

the sequence will be opened at the time each individual participant is randomly assigned to his or her condition. The randomization schedule will be stratified by family member relationship (spouse vs. non-spouse) and time since the relative's admission (3 months or less vs. over three months) to ensure balance on these important predictors of caregiver outcomes. Cases will be randomized within variable-sized blocks that range from 6 to 10 participants. No research staff or investigator interacting with potential participants will have access to the random assignment schedule, and, because of the variable block sizes and the sealed assignment envelopes, no person with participant contact will be able to determine the next treatment assignment in the sequence. These procedures accomplish both random treatment assignment and treatment allocation concealment throughout the trial, and are consistent with the recommendations of the CONSORT statement (see <http://www.consort-statement.org/>). The RC will inform the ADRD caregiver of their randomization status as soon as possible following completion of the baseline interviews.

-Study schedule: Months 3-44 (see Figure below)

-Time for participants: approximately 10 minutes

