17.0 Statistical Considerations

17.1 Data Analysis Plan:

Analysis of Specific Aims 1-3

Data available at baseline, 4 months, 8 months, and 12 months will allow for individual growth curve models that examine change in ADRD caregiver outcomes.^{103,104} Multilevel analysis approaches are available that support growth curve modeling. In this context, growth curve modeling is an example of a 2-stage modeling process consisting of 1) a within-subjects model across time, and 2) a between-subjects model that incorporates caregiver and person with ADRD covariates.^{105,106} The primary independent variable in the proposed investigation consists of an indicator variable for random assignment into the RCTM treatment condition or the attention care control. [SAS (version 9.4) Proc Mixed¹⁰⁷] will be used to conduct these analyses, as it supports multilevel and growth curve modeling procedures.

Our proposed analyses will provide in-depth tests of Specific Aims 1 to 3 (i.e., rates of change in primary subjective stress, secondary role strains, residential care stress, and caregiver depressive symptoms) over a 12-month period. In one set of outcome evaluations, the baseline value will be included as a covariate, and time will be “centered” at 4-months post-baseline. This scales the intercept effect to be a main effect of RCTM group assignment and allows the RCTM treatment and the attention control groups to have different 4-, 8-, and 12-month change trajectories, or an RCTM treatment*time interaction effect. After establishing that the individual growth parameter estimates have significant variance around the mean trajectories of change in key dependent variables, an RCTM treatment vs. control group indicator will be added as the key independent variable to predict intercepts and rates of change in outcomes. Additional analyses will determine if covariates (e.g., context of care indicators, primary objective stressors, and resources) significantly vary across the RCTM treatment and control groups at baseline and over time via growth curve modeling procedures. If statistically significant variations between the RCTM treatment and control groups are found, initial status and rate of change parameters for these covariates will be included in all tests to provide further statistical control.

SOCIAL PROTOCOL (HRP-580)

PROTOCOL TITLE: The Residential Care Transition Module

VERSION DATE: 2/10/2022

Secondary Analyses

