In addition to analyses of secondary Aims 1a and 1b (which will mirror the Specific Aims 1-3 analyses described above), empirical treatment fidelity data on variations in use of RCTM (e.g., frequency and duration of counseling sessions) will be included in growth curve models as a series of post-hoc Specific Aims 1, 2, and 3 analyses. These analyses will explore the effects of variations in RCTM utilization on the outcomes hypothesized above. [A series of mediational models will also be tested examining some of the hypothesized pathways of the SPM-RC as described in the conceptualization of the proposed project (e.g., whether RCTM assignment mediates the empirical relationships between care-related stressors and more global psychological and emotional outcomes on the part of family caregivers). As detailed by Selig and Preacher and other methodologists, mediational models appropriate for longitudinal data will be utilized.¹⁰⁸ These analyses will explore the empirical mechanisms that explain RCTM's efficacy or lack thereof.]

Specific Aim 4 Analyses

Specific Aim 4 analyses will primarily focus on thematic content analysis of open-ended data to examine RCTM utility and mechanisms of benefit. Systematic reading and rereading of qualitative content and hand coding of a significant proportion of this content is necessary in order to develop an understanding of meanings in their conversational or observational contexts.^{109,110} Specifically, the PI, [name] (Co-Investigator) and the research assistants will independently develop coding categories together with descriptors (via hand-coding and NVivo) and will develop a shared coding scheme that will reflect the primary categories of the transcription. Through repetition of this procedure, a consensus perspective on appropriate coding categories and themes will be modified and developed. These themes will provide insights as to the RCTM's implementation and use (i.e., treatment fidelity/process evaluation) and mechanisms of benefit (i.e., semi-structured interview embedded component).

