Intensive longitudinal analysis procedures (multilevel regression analyses of outcome and growth curve modeling) will be utilized to capitalize on the randomized controlled design and the multiple waves of data to be collected. The number of ADRD caregivers to be enrolled to address study hypotheses was determined using power analysis procedures that take into account the hierarchical analytic design of the study.⁹⁹ In this framework, the researcher identifies the Type I error rate (e.g., $p < .05$) to differentiate between a null and alternative test hypothesis, a suitable level of statistical power (.80 is considered an excellent power value), and the expected difference between the two study groups in order to determine the number of ADRD caregivers to enroll into the project. [We sought a sample size that would be sufficient to detect a group difference of 0.50 standard deviation units and modest effect sizes that we identified in our preliminary efficacy trial. This is considered to be a “medium” effect size¹⁰⁰ and is a reasonable benchmark to evaluate the efficacy of a behavioral intervention in comparison to a usual care control condition. We also used a Bonferroni adjusted Type I error rate of .0125 (.05/4) to accommodate up to 4 primary outcome variables (primary subjective stress; secondary role strain; residential care stress; caregiver depressive symptoms), and we allowed for a conservative 10% loss to follow-up. With these specifications, an enrolled sample size of 240 ADRD caregivers (120 in each group) was sufficient to provide adequate statistical power. After attrition, this sample size will give us .87 power to detect a 0.50 effect size and .80 power to detect a slightly smaller effect size of 0.46 standard deviation units. This effect size could apply to covariate-adjusted mean differences at a particular follow-up point, or two linear slope differences of change across time between the intervention and control conditions.]

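### Randomisation is stratified by spouse status and time since admission, but section 17.1 does not commit to either factor in the baseline-adjusted models; naming them is a minor, nearly free gain in precision

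*Combined protocol and SAP*

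**What the plan says.** Section 5.2 (Treatment/Intervention Period) describes 1:1 allocation in variable blocks of 6 to 10. The schedule is "stratified by family member relationship (spouse vs. non-spouse") and by "time since the relative's admission (3 months or less vs. over three months"). The stated purpose is "to ensure balance on these important predictors of caregiver outcomes".

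Section 17.1 sets out the Aims 1-3 models. It commits to treatment group, time, their interaction and, for some models, the outcome at baseline: "In one set of outcome evaluations, the baseline value will be included as a covariate", with time centred at 4 months so that the group term is a main effect at that visit. Three other statements bear on covariates:

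- The second stage is "a between-subjects model that incorporates caregiver and person with ADRD covariates". No covariate is named there.
- Covariates found to differ significantly between arms are added: "initial status and rate of change parameters for these covariates will be included in all tests".
- The Aims 1a and 1b analyses are ones "which will mirror the Specific Aims 1-3 analyses described above", so they inherit the same specification.

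Section 17.2 says that its effect size may refer to "covariate-adjusted mean differences at a particular follow-up point", again without saying which covariates. Neither 17.1 nor 17.2 mentions spouse status, time since admission or stratification factors as model terms.

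**The concern.** Blocking within strata removes the between-stratum part of the chance difference between arms, so the group contrast has a smaller true variance. A model that omits the strata leaves that variation in its residual and reports the larger variance. The 4-month group test is then somewhat conservative and its confidence interval somewhat too wide. The design pays for the balance, and the analysis does not collect the benefit.

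The significance-triggered rule does not close the gap. Its reference to starting level and rate of change suits covariates measured repeatedly, so it does not clearly govern two factors fixed at randomisation. If it were applied to them at baseline, a factor balanced by design could hardly qualify, however prognostic it is. Including and omitting the strata are therefore both compatible with the present wording, and the two choices can give different standard errors for each outcome tested at .0125.

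**Working it through.** **1. Inputs.** From 17.2: 240 enrolled, 120 per arm; 10% loss, so 120 x 0.9 = 108 per arm; alpha .05/4 = .0125; effects of 0.50 and 0.46 SD. Sidedness is not stated; two-sided is assumed because it reproduces the stated power. Assumed, because the documents give no figure: R², the share of outcome variance left after the baseline outcome that the two factors explain, at 2%, 5% and 10%.

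**2. The plan's own figures.** SE = sqrt(2/108) = 0.1361 SD; critical value 2.498; power = Phi(d/SE - 2.498).

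- d = 0.50: 3.674 - 2.498 = 1.176, power .880 (.875 by noncentral t, 214 df). Stated .87.
- d = 0.46: 3.380 - 2.498 = 0.883, power .811 (.805 by t). Stated .80.

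Both reproduce. One-sided .0125 would give .924 and .873, which do not match.

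**3. Closed form for the group main effect, exact balance.** Write k = 1/sqrt(1 - R²).

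- Reported SE without the strata, relative to the true SE: k
- True type I error without the strata: 2[1 - Phi(2.498k)]
- Power without the strata: Phi[(d/0.1361 - 2.498)k]
- Power with the strata: Phi[(d/0.1361)k - 2.498]

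For R² = .10, k = 1.054. Type I error: 2.498 x 1.054 = 2.633, giving .0085. Power at 0.46 SD without the strata: 0.883 x 1.054 = 0.930, giving .824. With them: 3.380 x 1.054 - 2.498 = 1.065, giving .857.

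| R² | SE too wide | Type I error, strata omitted | Power at 0.46, omitted | Power at 0.46, included |
|---|---|---|---|---|
| 0 | 0% | .0125 | .811 | .811 |
| .02 | 1.0% | .0116 | .814 | .820 |
| .05 | 2.6% | .0104 | .817 | .834 |
| .10 | 5.4% | .0085 | .824 | .857 |

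**4. Simulation of a longitudinal model.** 16,000 trials per R² value, N = 240, stratified blocks of 6/8/10, 10% random loss, visits at 4, 8 and 12 months, baseline-adjusted REML fit with unstructured covariance, strata as main effects. The spouse share is 17/36, from the pilot in section 2.2. The share admitted within three months (.40) and the variance components are assumed.

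| R² | Reported/empirical SE, omitted (MC SE .006) | Type I error, omitted (MC SE .0009) | Power at 0.46, omitted | Power at 0.46, included |
|---|---|---|---|---|
| 0 | .997 | .0114 | .831 | .832 |
| .02 | 1.000 | .0124 | .834 | .841 |
| .05 | 1.015 | .0101 | .840 | .857 |
| .10 | 1.041 | .0102 | .849 | .880 |

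A different model is fitted here, so the power levels differ from step 3. The gap between the two power columns is the result of interest: 0.7, 1.7 and 3.1 points for R² of .02, .05 and .10. A second simulation (5,000 trials per value, N = 216, other assumed stratum shares) gave reported/empirical SE of 1.001, 1.010, 1.019 and 1.050.

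**5. Treatment-by-time slope.** The SE ratio without versus with the strata is 1.000 throughout. A main effect that is constant over time does not enter a within-person slope.

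**6. Would the imbalance rule admit the factors?** Taking 5% as the level (17.1 gives none), a baseline chi-square test was significant on either binary factor in 0 of 24,000 stratified-block allocations. This check does not cover differential dropout or time since admission as a continuous variable.

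**7. Cost if the factors are useless.** At R² = 0 the SE ratio without versus with the strata is .9995, so adding them widens the SE by about 0.05%.

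**The case against.** The best case for leaving the plan alone has four parts.

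- **The plan is arguably not silent.** The between-subjects stage already takes in caregiver covariates, and spouse status is plainly one. This stands as far as it goes. A reader might infer that 17.1 excludes the strata, and the documents do not support that. But permission is not commitment.
- **The size is assumed.** No document gives prognostic strength. Section 2.2 singles out husbands for depression, whereas the stratum pools husbands with wives; for burden it names both wives and daughters, which is no spouse contrast. Section 4.1 places the risk in the months after entry but gives no three-month cut. Only the phrase in 5.2 supports prognostic value directly, and it is not quantified. This stands: the effect may be zero, and at R² = .02 the simulation in step 4 shows no detectable excess in the reported SE.
- **Much of the testing gains nothing.** Section 17.1 frames Aims 1-3 largely as rates of change, and the slope SE does not move. This also stands and confines the point to the group main effect.
- **It is late.** This version is dated 2/10/2022, and section 8.1 gives a parent project period ending 05/31/2021. Even a change involving only design factors needs documenting.

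A reader might also want the baseline outcome required as a covariate in every model. Section 17.1 does not support that. It uses baseline this way in one set of evaluations only, and it also describes growth curves on data that include the baseline wave, where baseline could not sensibly be outcome and covariate at once.

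**Conclusion.** The point holds as a minor, optional improvement. Section 17.1 does not commit to the two stratification factors, and its imbalance rule would almost never bring them in. If they explain 2-10% of the variance left after baseline (assumed), the reported SE of the group main effect in the baseline-adjusted models is about 0-5% too wide, and power at 0.46 SD is about 1-3 points below what the same data could give. The closed form sits at the upper end because it assumes exact balance; the 16,000-trial simulation gives about 0-4%.

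Stronger readings fail. A reader might infer bias, an invalid test or an underpowered trial. Omitting the strata does not bias the estimate. Any error in the test is on the conservative side, and the stated .87 and .80 power does not depend on the strata.

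**What to change.** In 17.1, state that the baseline-adjusted Aims 1-3 models, and the 1a and 1b models that mirror them, include spouse/non-spouse and time since admission (the two categories used at randomisation, as randomised) as fixed covariates whatever the observed balance. Leave the handling of the baseline outcome in the plan's other models unchanged.

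The cost is two degrees of freedom out of more than 200 and no new data, since both factors are recorded at randomisation. The change should carry a dated note made before the outcome analysis.

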7.0 Sharing of Results with Participants

7.1 When manuscripts are published, the findings will be distributed to all research participants. Main outcome papers that address the study aims will not be disseminated until all data collection procedures are completed. However, analyses of treatment receipt, perceived utility, important aspects of intervention delivery, and other descriptive analyses have and will be disseminated prior to the main outcome papers. The project team aims to minimize the length of time between final data collection procedures and dissemination of final outcome papers to appropriate peer-reviewed journals. We anticipate a timeframe of 6 months between final data collection and peer-reviewed article submissions of RCTM outcomes.

SOCIAL PROTOCOL (HRP-580)

PROTOCOL TITLE: The Residential Care Transition Module

VERSION DATE: 2/10/2022

8.0 Study Duration

8.1 ADRD caregivers will participate in the parent study for about 12-months; the total project duration is 5 years (06/01/2016 - 05/31/2021). This will be extended for the COVID-19 administrative supplement for one year beyond the originally planned timeline. A project timeline is below:

Project Timeline

	Months 1-3	Months 4-12	Months 13-55	Months 56-60	Months 60-62
Data management processes	●	○	○	○	○
Hiring and training of research coordinator and 2 research assistants	●	○	○	○	○
Monthly research team meetings/Project management	●	●	●	●	●
Recruitment of ADRD caregivers [(n = 240)]	●	●	●		
Re-enrollment of previous RCTM participants (up to N = 113) to take part in supplemental COVID-19 surveys					●
Administration of Residential Care Transition Module counseling sessions		●	●	○	
Baseline, 4-, 8-, and 12-month data collection		●	●	○	
Treatment fidelity/process evaluation		●	●	●	
Embedded semi-structured interviews, post evaluation			●	●	●
RCT longitudinal analysis; Analysis of post-RCT embedded component			●	●	
Dissemination			○	●	●

NOTE: ADRD = Alzheimer's disease or a related dementia; RCT = randomized controlled trial;

LEGEND: ● = primary focus; ○ = ongoing but less intensive

9.0 Study Population

9.1 Inclusion Criteria: Eligibility criteria include family caregivers who consider themselves the most involved in visiting and providing assistance to the person with memory loss (or who share the primary caregiving role equally). For the caregiver to participate, the care recipient must be residing in a RLTC setting (e.g. assisted living, nursing home, memory care, or other residential long-term care setting) and have received a physician's diagnosis of ADRD. Family caregivers must be English speaking, 21 years of age or older, and not participating in any other one-to-one psychosocial consultation specifically for caregiving (support group participation is not a deterrent to enrollment, nor is general counseling not specific to caregiving). Family caregivers on psychotropic medications, such as anti-depressants or anti-psychotics, will be eligible if they have remained on a stable dosage for the last 3 months.

The sample for the administrative supplement focused on COVID-19 will be drawn from participants in the original RCTM parent study. Caregivers who have already completed the study and who have not previously reported bereavement, as well as those caregivers who remain currently enrolled in the parent study, will be invited to take part in the proposed supplemental assessments. Among previously-completed participants, those whose care recipient is still alive will be eligible to re-enroll. Among currently-enrolled participants, any who are not bereaved, or who are bereaved but have been continuing to participate in

SOCIAL PROTOCOL (HRP-580)**PROTOCOL TITLE: The Residential Care Transition Module****VERSION DATE: 2/10/2022**

bereavement-modified surveys, will be eligible to participate in supplemental surveys. Both control and treatment group participants will be eligible. Previously-completed caregivers whose care recipient has already passed away will not be eligible to enroll in the supplement.

9.2 Exclusion Criteria: Caregivers are not eligible to participate if they do not meet the inclusion criteria above.

9.3 Screening: If caregivers are interested in participating, the RC will conduct a brief screening procedure using the RCTM Screening Form, developed on the above eligibility criteria.

Previously completed participants who are interested in participating in the additional survey(s) for the COVID-focused supplement will complete a brief screening survey prior to re-enrollment, including items assessing bereavement

10.0 Vulnerable Populations

10.1 Vulnerable Populations:

Population / Group	Identify whether any of the following populations will be primary focus of the research (targeted), included but not the focus of the research or excluded from participation in the study.
Children	Excluded
Pregnant women/fetuses/neonates	included but not the focus
Prisoners	Excluded
Adults lacking capacity to consent and/or adults with diminished capacity to consent, including, but not limited to, those with acute medical conditions, psychiatric disorders, neurologic disorders, developmental disorders, and behavioral disorders	included but not the focus; see Sections 10.2 and 22.6 for descriptions and safeguards
Non-English speakers	Excluded
Those unable to read (illiterate)	Excluded
Employees of the researcher	Excluded
Students of the researcher	Excluded

SOCIAL PROTOCOL (HRP-580)**PROTOCOL TITLE: The Residential Care Transition Module****VERSION DATE: 2/10/2022**

Undervalued or disenfranchised social group	included but not the focus
Active members of the military (service members), DoD personnel (including civilian employees)	included but not the focus
Individual or group that is approached for participation in research during a stressful situation such as emergency room setting, childbirth (labor), etc.	Excluded
Individual or group that is disadvantaged in the distribution of social goods and services such as income, housing, or healthcare.	included but not the focus
Individual or group with a serious health condition for which there are no satisfactory standard treatments.	included but not the focus
Individual or group with a fear of negative consequences for not participating in the research (e.g. institutionalization, deportation, disclosure of stigmatizing behavior).	Excluded
Any other circumstance/dynamic that could increase vulnerability to coercion or exploitation that might influence consent to research or decision to continue in research.	Excluded

